Grade 2 (≥ 2.00 to 3.0 × ULN or 2.0 to 3.0 × baseline)	
 
Hold dose of infigratinib until resolved to Grade ≤ 1 or baseline
 
If resolved within ≤ 7 days, maintain dose level of infigratinib
 
If resolved between > 7 days and 14 days, decrease by 1 dose level of infigratinib
 
If not resolved within ≤ 14 days, discontinue infigratinib
 
					
Grade ≥ 3 (> 3.0 × ULN or > 3 × baseline)	Discontinue infigratinib					
	INVESTIGATIONS – HEPATIC					
AST or ALT						
Grade 3 (> 5.0 to 20.0 × ULN) without bilirubin elevation > 2.0 × ULN	Hold dose of infigratinib until resolved to CTCAE Grade ≤ 1 or baseline  • If resolved within ≤ 7 days, decrease by 1 dose level of infigratinib  • If not resolved within ≤ 7 days, discontinue infigratinib					
Grade 4 (> 20.0 × ULN) without bilirubin elevation > 2.0 × ULN	Discontinue infigratinib					
AST or ALT and Bilirubin						
AST or ALT > 3.0 to 5.0 × ULN and total bilirubin > 2.0 × ULN without liver metastasis or evidence of disease progression in the liver	
 
Hold dose of infigratinib until both transaminases and bilirubin resolved to CTCAE Grade ≤ 1 or baseline.
 
If resolved within ≤ 7 days, decrease by 1 dose level of infigratinib.
 
If not resolved within ≤ 7 days, discontinue infigratinib
 
					
AST or ALT > 5.0 × ULN and total bilirubin > 2.0 × ULN	Discontinue infigratinib					

**Table 6.** Criteria for Interruption and Re-initiation of Infigratinib for AEs Considered to be Possibly Related to Infigratinib

Worst Toxicity CTCAE (v5.0) Grade (Unless Otherwise Specified)	Recommended Dose Modifications any Time During a Cycle of Therapy						
LABORATORY / METABOLIC DISORDERS							
Asymptomatic Amylase and/or I	ipase Elevation						
present, consider a CT scan or oth	nptoms of acute pancreatitis (abdominal pain or tenderness), and, if er imaging study to assess the pancreas, liver, and gallbladder to creatitis and assess for complications.						
Grade 3 (> 2.0 to 5.0 × ULN)	Hold dose of infigratinib until resolved to CTCAE Grade ≤ 2						
	decrease by 1 dose level of infigratinib						
	
 
If not resolved within ≤ 14 days, discontinue infigratinib
 
						
	For recurrent Grade 3 asymptomatic lipase or amylase elevation despite dose reduction, infigratinib should be held and continuation of therapy should be discussed with the medical monitor following resolution to ≤ Grade 2.						

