#### 10. MEASUREMENTS

### 10.1 Primary endpoint:

The primary endpoint is the incidence of dose-limiting toxicities (DLTs) in the first 2 cycles of therapy at a specific dose. In Cohort 1, in a subset of subjects who start at infigratinib 100 mg and complete 2 cycles with no DLTs and who remain on study for Cycles 3 and 4, the dose of infigratinib will be increased to 125 mg starting with Cycle 3 and the number of DLTs in Cycles 3 and 4 will be counted toward the primary endpoint (for the 125 mg dose), in addition to the number of DLTs in Cycles 1 and 2 (for the 100 mg dose). For all other subjects, the primary endpoint will be the number of DLTs in Cycles 1 and 2.

DLTs will be graded using NCI CTCAE (Common Terminology Criteria for Adverse Events), v5.0. DLTs will be defined as an adverse event (AE) or abnormal laboratory value at least possibly related to therapy with infigratinib including those AEs and abnormal laboratory values that result in a failure to meet the criteria for re-treatment. The criteria for defining a DLT, which are pre-specified based on the pre-clinical toxicity of infigratinib, are listed in Table 7.

Individual subjects who had a DLT may be retreated, after recovery, at the next lowest dose level.

Investigators will notify QED Therapeutics within 7 days of any DLTs observed.

**Table 7.** Criteria for defining dose-limiting toxicities

TOXICITY	DLT CRITERION
Skipped/ delayed dose	The inability to administer infigratinib on ≥ 75% of scheduled treatment days during cycle 1 at that dose (ie, ≥ 16 days of the 21 days of planned treatment) due to unresolved adverse event of any grade and considered at least possibly, probably, or definitely related to the study drug.
	Delay in 2 nd cycle administration at that dose due to failure of recovery from a possibly, probably, or definitely related adverse event to Grade ≤ 1 or baseline by Day 43 (Day 28 of Cycle 1 + 15 days), except for alopecia.
Blood/ bone marrow	Neutropenia     • Febrile, CTCAE Grade ≥ 3.     • CTCAE Grade ≥ 3 for > 7 consecutive days
	Thrombocytopenia
	Anemia CTCAE Grade 4
Renal/ genitourinary	Creatinine:  • CTCAE Grade 1 for > 7 consecutive days and serum inorganic phosphorus  > 5.5 mg/dL and/or serum total calcium x serum inorganic phosphorus  > 55 mg²/dL² and despite phosphorus lowering therapy for ≥ 14 days
	
 
CTCAE Grade 2 for > 7 consecutive days
 
CTCAE Grade ≥ 3
 

**Table 7.** Criteria for defining dose-limiting toxicities

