### 10.2 Secondary endpoints:

- 1. Incidence of treatment-emergent adverse events (TEAE). A TEAE is defined as an adverse event with initial onset or increasing in severity after the first dose of study treatment until 30 days after last dose of study drug. TEAEs will be assessed and documented at each scheduled or unscheduled visit during the reporting period. Each TEAE will be assessed according to whether it is serious or non-serious, whether it is expected or unexpected according to the Investigator's Brochure, and whether it is related or unrelated to the study treatment. Each TEAE will be assigned a grade according to CTCAE v5.0. A serious adverse event is one that results in death, is life-threatening, requires in-patient hospitalization or causes prolongation of existing hospitalization, results in persistent or significant disability/incapacity, may have caused a congenital anomaly/birth defect, or requires intervention to prevent permanent impairment or damage. Pregnancy during the reporting period will be classified as a serious adverse event.
- 2. Objective tumor response, per RECIST v1.1 (see Appendix C), in subjects with measurable disease. An objective tumor response can be observed at any time on study between 8 weeks after starting therapy (C3D1) through 18 months after starting therapy.
- 3. Progression-free survival (PFS), defined as the number of days to either progressive disease as defined per RECIST v1.1 or death.
- 4. Clinical benefit, defined as an objective tumor response or stable disease at 6 months, defined per RECIST v1.1 (see Appendix C).

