# 10.3.2 Secondary Outcomes

1. **Outcome Title**: Treatment-emergent Adverse Events (TEAE)

**Outcome Measure Description**: Treatment-emergent adverse events (TEAEs) are defined as adverse events of any grade with initial onset or increasing in severity after the first dose of study treatment until 30 days after last dose of study drug. Pregnancy during the reporting period will be classified as a serious adverse event. The outcome will be expressed as the number of events by the infigratinib dose level at the time of the event, stratified by relatedness and Common Terminology Criteria for Adverse Events (CTCAE) grade. The result is a number without dispersion.

**Time Frame**: 2 years

2. Outcome Title: Objective Tumor Response

**Outcome Measure Description**: Objective tumor response will be assessed as achieving a Response Evaluation Criteria in Solid Tumors (RECIST) v1.1 Complete Response (CR) or a Partial Response (PR). The outcome will be reported as the number of subjects by each participant's final infigratinib dose level that achieve an overall response (OR) to treatment, ie, CR or PR, within 18 months of starting treatment. The outcome will be reported as a number without dispersion. RECIST criteria are:

- CR = Disappearance of all target lesions
- PR =  $\geq$  30% decrease in the sum of the longest diameter of target lesions
- Overall Response (OR) = CR + PR
- Progressive disease (PD) = 20% increase in the sum of the longest diameter of target lesions, and/or the appearance of one or more new lesion(s)
- Stable disease (SD) = Small changes that do not meet any of the above criteria

**Time Frame**: up to 18 months

3. **Outcome Title**: Progression-free Survival (PFS)

**Outcome Measure Description**: Progression-free survival (PFS) means the subject is alive without return or relapse of the tumor. The outcome is defined as the number of

days to either progressive disease as defined per RECIST v1.1 or death, by each participant's final infigratinib dose level, and reported as the median PFS with full range. RECIST criteria are:

- CR = Disappearance of all target lesions
- PR = ≥ 30% decrease in the sum of the longest diameter of target lesions
- Overall Response (OR) = CR + PR
- Progressive disease (PD) = 20% increase in the sum of the longest diameter of target lesions, and/or the appearance of one or more new lesion(s)
- Stable disease (SD) = Small changes that do not meet any of the above criteria

Time Frame: Up to 2 years.

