4. **Outcome Title**: Clinical Benefit

**Outcome Measure Description**: Clinical benefit will be assessed as achieving a Response Evaluation Criteria in Solid Tumors (RECIST) v1.1 Complete Response (CR); Partial Response (PR); or Stable Disease (SD). The outcome will be reported as the number of subjects by each participant's final infigratinib dose level that achieve a CR; PR; or SD, within 6 months of starting treatment. The outcome will be reported by treatment and dose level as a number without dispersion. RECIST criteria are:

- CR = Disappearance of all target lesions
- PR = ≥ 30% decrease in the sum of the longest diameter of target lesions
- SD = Small changes that do not meet any of the above criteria
- Progressive disease (PD) = 20% increase in the sum of the longest diameter of target lesions, and/or the appearance of one or more new lesion(s)
- SD = Small changes that do not meet any of the above criteria

Time Frame: up to 6 months

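### Section 10.3.2 reports response, PFS and clinical benefit by final infigratinib dose, which depends on time on treatment, so results by dose can differ with no dose effect

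*Combined protocol and SAP*

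**What the plan says.** Section 10.3.2 uses one grouping for three efficacy outcomes. PFS is given by each participant's "final infigratinib dose level, and reported as the median PFS with full range". Response counts subjects by "final infigratinib dose level that achieve an overall response (OR) to treatment". Clinical benefit counts them by "final infigratinib dose level that achieve a CR; PR; or SD, within 6 months of starting treatment". Safety outcomes are grouped differently: DLTs by assigned dose (10.3.1), and adverse events by the dose in use when the event occurs (10.3.2).

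The rules that set the final dose are elsewhere:

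- **Escalation.** Under 10.1, the dose rises from 100 to 125 mg at Cycle 3 for subjects who "complete 2 cycles with no DLTs and who remain on study for Cycles 3 and 4". Section 12.4 has the same rule. Neither makes escalation wait for a scan result.
- **First scan.** The Study Calendar (Section 9) puts it at Cycle 3 Day 1, with a window of up to 7 days afterwards. Section 10.2 counts responses from that visit on.
- **Reductions.** Section 6 allows two from 125 mg and one from 100 mg, at any point in a cycle.
- **After a DLT.** Section 10.1 says: "Individual subjects who had a DLT may be retreated, after recovery, at the next lowest dose level". For some toxicities Table 6 ends treatment instead, for example raised AST or ALT: "If not resolved within ≤ 7 days, discontinue infigratinib".
- **Progression.** Section 4.2 lists it as a reason to stop treatment.

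Section 12.6 lists the maximum dose received and plans Kaplan-Meier plots of PFS overall and by IC2 and IC6, not by dose. Section 12.1 calls the analysis mainly descriptive, and the Synopsis gives 3 to 12 evaluable subjects.

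**The concern.** Final dose is formed during follow-up, partly by the outcome itself. Two mechanisms pull in different directions.

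- **Escalation.** A 100 mg starter who ends at 125 mg must have stayed on study for 56 days. One who leaves before Cycle 3 without a DLT is counted at 100 mg. This is immortal-time bias and favours 125 mg.
- **Reduction.** The longer a subject stays on treatment, the more chances there are to be reduced. Long-staying subjects drift towards 75 mg, which makes low doses look better.

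Response adds a misattribution. A response first seen at Cycle 3 Day 1 follows two cycles at 100 mg, but is credited to 125 mg if the subject escalates and ends there.

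Section 10.3 says that the registry outcomes stand for the study objectives. A reader of the posted table could take differences made by the grouping rule for a dose-response pattern.

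**Working it through.** **1. The plan's own figure.** The rules in 12.4 reproduce the sample size. The minimum of 3 is 0 of 3 DLTs at 100 mg, with the same three escalating and 0 of 3 at 125 mg. The maximum of 12 is 3 + 3 at 100 mg, then 3 + 3 at 75 mg. So at most six subjects start at 100 mg, replacements aside.

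**2. Inputs, with no dose effect.**

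- Median PFS m = 5.5 months at every dose, an assumption borrowed from the placebo arm of the fulvestrant trial in 2.3.1. At 30.4375 days per month, m = 167.4 days.
- DLT risk 1/6 at 100 mg and 1/8 at 125 mg, from the single-agent data in 2.2.9; 1/6 at 75 mg is assumed.
- Scans every 56 days. PFS is exponential, independent of dose and toxicity, and recorded at the next scan.
- Later reductions: an assumed probability per 28-day cycle from Cycle 3, floor 75 mg. The documents give no rate, so 0, 2% and 10% are shown.

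**3. By hand: escalation only, scan read first.**

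- Progressing by day 56: 1 − 2^(−56/167.4) = 20.7%. Without a DLT, these subjects stay at 100 mg, and progression is recorded at 56 days = 1.8 months.
- Escalated subjects: median 56 + 167.4 = 223 days, recorded at the fourth scan, 224 days = 7.4 months.
- True value on the same scan grid: 168 days = 5.5 months.

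One scan step is 56/30.4375 = 1.84 months, and 167.4 days lies almost on the third scan. A difference of one step should not be over-read.

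**4. Simulation following the enrolment rules in 12.4.**

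| Later reductions per cycle | Scan and escalation | Median PFS by final dose (months) |
|---|---|---|
| 0 | scan read first | 125 mg: 7.4; 100 mg: 1.8 |
| 0 | escalation first | 125 mg: 5.5; 100 mg: 5.5 |
| 10% | either order | 75 mg: 9 to 11; 125 mg: 3.7 to 5.5 |

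The ranges also cover a subject with a DLT either continuing one level lower or stopping.

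At the level of single trials:

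- At 10% per cycle, the 75 mg median exceeds the 125 mg median in about 74–84% of trials where both groups exist, which is about 47–64% of trials.
- At 2% per cycle, it does so in about 41–55%. With no bias the figure would be near one half, slightly less because of ties, so chance dominates.
- At 10% per cycle, the 125 mg median exceeds the 100 mg median in about 52% of trials if the scan is read first and in 18–19% if not. That direction is not fixed.

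**5. Check of the remedy.** Grouped by starting dose under the same no-effect assumption, the 100 and 125 mg groups both give 5.5 months, with or without later reductions and in either scan order. In continuous time they give 167 against 167 days.

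**6. Clinical benefit, a separate matter.** Section 10.2 asks for "an objective tumor response or stable disease at 6 months"; 10.3.2 counts CR, PR or SD reached within 6 months. If every subject not progressing at the first scan counts under 10.3.2, the share is 1 − 0.207 = 79%. If 10.2 is approximated by being progression-free past week 24, it is 2^(−168/167.4) = 50%. The same subjects give different counts.

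**The case against.** The strongest reply is that nothing is decided on this table. The secondary objectives are to estimate, not to compare doses. Section 12.6 lists individual histories and plots PFS without regard to dose, and 12.4 and 12.9 select the dose on DLTs alone. Under 12.4, six or fewer subjects are enrolled in roughly 74–83% of simulated trials and twelve in about 5%, so the listings show most of what there is to see. All of this stands and limits the point to minor. It does not make the grouping interpretable, because 12.6 does not replace the table in 10.3.2.

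It can also be said that the calendar makes escalation before the scan result more likely, since the window runs only after Cycle 3 Day 1. In that order, with no later reductions, there is no distortion. This is fair: the size then rests on a reduction rate that the documents do not give. The 5.5-month median comes from another regimen, and 1/6 is one event in six subjects.

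Three stronger readings are tempting and not supported:

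- **That the table systematically favours 125 mg.** Later reductions work the other way.
- **That almost any trial would show 75 mg above 125 mg.** Starting twelve subjects at 100 mg gives 77–98% at 10% reductions per cycle, but 12.4 does not allow that design.
- **That censoring is ignored for PFS.** The median with full range in 10.3.2 leaves this unsaid, but 12.6 already plans Kaplan-Meier, so it is mostly missing detail.

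**Conclusion.** The concern holds as a minor point. Final dose depends on time on treatment, so response, PFS and clinical benefit by final dose can differ between doses when dose does nothing, and no other section corrects this. Confidence is high for that qualitative statement. The sizes are illustrations that rest on the assumed PFS, DLT and reduction rates and on PFS being independent of toxicity. They run from no distortion (escalation before the scan is read, no later reductions) to several months between dose groups.

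A reader might infer that the recommended dose is at risk. It is not: selection uses DLTs, and the Kaplan-Meier plots in 12.6 are not by dose. The harm is confined to the posted descriptive table. The conflict between the two clinical-benefit definitions is real but separate, and would survive any regrouping.

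**What to change.** In 10.3.2, report response, PFS and clinical benefit overall and by starting dose, defined as the infigratinib dose at Cycle 1 Day 1. The term assigned dose is better avoided here, because 10.1 counts the Cycle 3 and 4 DLTs of escalated subjects at 125 mg. Show final and maximum dose only as listing columns. Give PFS as the Kaplan-Meier median with the number censored, in line with 12.6. Separately, reconcile 10.2 and 10.3.2 on clinical benefit and state which definition applies.

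The cost is wording only; no new data and no change to treatment are needed. The downside is that time spent at 125 mg after escalation is credited to the 100 mg starting group. If nobody starts at another dose, the starting-dose table equals the overall result. A landmark analysis at Cycle 3 Day 1 would also remove the bias, but is out of proportion with so few escalated subjects and is not needed.

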# **PROTOCOL SYNOPSIS**

TITLE	A Phase 1B Study of Infigratinib in Combination with Tamoxifen in Hormone Receptor-Positive, HER2-Negative FGFR-Altered Advanced Breast Cancer
STUDY PHASE	1B
INDICATION	Advanced breast cancer, ER and/or PR + , HER2  . Additional inclusion and exclusion criteria outlined in n Section 3.1 and Section 3.2.
INVESTIGATIONAL PRODUCT	Cohort 1: Infigratinib + Tamoxifen
PRIMARY OBJECTIVE	Identify the recommended dose of infigratinib to be used in combination with the FDA-approved dose and schedule of tamoxifen.
SECONDARY OBJECTIVES	
 
Estimate the incidence of treatment-emergent adverse events.
 
Estimate the objective tumor response rate.
 
Estimate progression-free survival.
 
Estimate the clinical benefit rate.
 

EXPLORATORY OBJECTIVES	
 
Establish viable tumor-derived organoid cultures to study in vitro tumor response to combination targeted therapy.
 
Examine cell-free DNA from plasma across therapy to identify markers of therapeutic resistance.
 
Examine tumor and microenvironmental changes across therapy using in situ proteomics.
 

STUDY POPULATION	Eligible subjects will be adults with ER-positive and/or PR-positive, HER2-negative breast cancer and radiographic evidence of metastatic disease, or locally recurrent unresectable disease. Women must be postmenopausal. Due to length, the Eligibility Criteria are only presented in one instance. See Section 3 Participant Selection and Enrollment Procedures .

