#### Secondary endpoints:

Incidence of treatment-emergent adverse events Objective tumor response Progression-free survival Durable clinical benefit

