#### 1.2. Secondary Objectives

- Estimate the incidence of treatment-emergent adverse events (serious and non-serious).
- Estimate the objective tumor response rate (ORR) in subjects with measurable disease.
- Estimate the progression-free survival (PFS).
- Estimate the durable clinical benefit rate.

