#### Target disease

- Complete Response (CR): Complete disappearance of all target lesions with the exception
  of nodal disease. All target nodes must decrease to normal size (short axis < 10 mm). All
  target lesions must be assessed.

- Partial Response (PR): Greater than or equal to 30% decrease under baseline of the sum
  of diameters of all target measurable lesions. The short diameter is used in the sum for
  target nodes, while the longest diameter is used in the sum for all other target lesions. All
  target lesions must be assessed.
- Stable: Does not qualify for CR, PR or Progression. All target lesions must be assessed. Stable can follow PR only in the rare case that the sum increases by less than 20% from the nadir, but enough that a previously documented 30% decrease no longer holds.
- Objective Progression (PD): 20% increase in the sum of diameters of target measurable lesions above the smallest sum observed (over baseline if no decrease in the sum is observed during therapy), with a minimum absolute increase of 5 mm.
- Indeterminate: Progression has not been documented; and
  - One or more target measurable lesions have not been assessed; or

- o Assessment methods used were inconsistent with those used at baseline; or
- One or more target lesions cannot be measured accurately (eg, poorly visible unless due to being too small to measure); or
- One or more target lesions were excised or irradiated and have not reappeared or increased.

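### Section 10.3.2 counts stable disease reached within 6 months, while 10.2 requires it at 6 months, so one stable week-8 scan before progression counts only under 10.3.2

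*Combined protocol and SAP*

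**What the plan says.** Section 10.2, item 4, gives the endpoint: "Clinical benefit, defined as an objective tumor response or stable disease at 6 months, defined per RECIST v1.1".

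Section 10.3.2, outcome 4, gives the version for the trial registry. It counts subjects, by final infigratinib dose level, "that achieve a CR; PR; or SD, within 6 months of starting treatment", with "Time Frame: up to 6 months". It describes SD only as a small change that meets no other category. Appendix C likewise defines stable target disease as a state with no duration: "Does not qualify for CR, PR or Progression".

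The name of the endpoint also varies. Section 1.2 has "Estimate the durable clinical benefit rate" and the schema has "Durable clinical benefit". The synopsis has "Estimate the clinical benefit rate", and 10.2 also leaves out the word durable.

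Imaging (Section 9 and 10.2.2) is at baseline and every 8 weeks (± 7 days) from Cycle 1 Day 1. The first on-treatment scan is at Cycle 3 Day 1 with a + 7-day window. Section 10.3 states that the registry outcomes stand for the study objectives. Section 12.6 lists response at each scan, best response and progression date for each subject, but names no clinical-benefit analysis.

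**The concern.** Both definitions are current text and nothing in the protocol reconciles them. Under 10.2, SD has to be present at a landmark. Under 10.3.2, it has only to be seen once before that landmark. The first scan comes about four months before the 6-month point, so a single stable scan is enough for 10.3.2. That is hard to square with a benefit that the objectives and schema call durable.

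At stake is which number is reported. Section 10.3.2 is the text for public reporting, as a bare count per dose level without dispersion. A registry reader could not tell a subject stable for 8 weeks from one stable for 6 months. The per-subject listings in 12.6 would allow either count to be rebuilt, but only by someone who holds them.

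**Working it through.** There is no planned clinical-benefit rate or power figure to reproduce; 12.1 says that no formal method set the numbers per dose level. The check has two parts.

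**1. Apply each definition to possible scan sequences.** In 10.2 the 6-month condition may attach to SD only, or to both response and SD, so both readings are shown. For this table week 24 is taken as the 6-month assessment, PD is progressive disease, and PR is a response that has met any confirmation required by 10.2.2.

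| Weeks 8 / 16 / 24 | 10.2, condition on SD only | 10.2, condition on both | 10.3.2 |
|---|---|---|---|
| SD / PD / – | no | no | yes |
| SD / SD / PD | no | no | yes |
| SD / SD / SD | yes | yes | yes |
| SD / PR / PR | yes | yes | yes |
| PR / PD / – | yes | no | yes |
| PD / – / – | no | no | no |

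The first two rows split on either reading of 10.2. The fifth splits only if the condition covers response as well. No row counts under 10.2 and fails 10.3.2. A subject who first responds after week 24 was stable at week 24 if scans are complete, and so counts under both. The discrepancy therefore runs in one direction.

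**2. Illustrate the size.** Assume exponential progression-free survival, S(t) = 2^(−t/median). The two medians, 5.5 and 10.9 months, are those cited in 2.3.1 for the FGF-amplified subgroup of a randomized study of dovitinib with fulvestrant. They are not planning values for this trial.

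- Week 8 = 56/30.4375 = 1.84 months. Week 24 = 168/30.4375 = 5.52 months.
- Six months = 6 × 30.4375/7 = 26.1 weeks. The nearest scheduled scans are weeks 24 and 32, and the ± 7-day window on week 24 ends at week 25.
- Median 5.5: S(week 8) = 0.793, S(week 24) = 0.499, S(6 months) = 0.470. The gaps are 0.294 and 0.324.
- Median 10.9: S(week 8) = 0.890, S(week 24) = 0.704, S(6 months) = 0.683. The gaps are 0.186 and 0.207.

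The synopsis gives 3 to 12 evaluable subjects. For 12, the gaps are 3.5 to 3.9 subjects (median 5.5) and 2.2 to 2.5 (median 10.9). For 3, they are 0.9 to 1.0 and 0.6. A shorter assumed median of 3 months gives 0.654 − 0.250 = 0.404, or 4.8 of 12, so the range depends on the medians chosen.

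For given medians these are upper bounds. Some subjects who progress in the interval will have responded first. If the 6-month condition attaches to SD only, they count under both definitions and narrow the gap, by an amount the documents do not let us estimate. If it covers response too, they count only under 10.3.2 and the gap is not narrowed.

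**The case against.** The strongest reply is that little depends on this. It is a descriptive secondary count in a very small study, either version can be rebuilt from the 12.6 listings, and 10.3 ties the registry outcomes to the objectives, which favours 10.2. All of that stands, and it limits the weight of the point. It does not settle the definition: 10.3 does not say which text governs, and the word durable appears in some places and not others. The character-limit remark in 10.3.1 concerns only the dose-limiting toxicity outcome.

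It could also be said that within 6 months was meant as sustained to 6 months. The wording describes reaching a status inside a window, in the same form that 10.3.2 uses for tumor response within 18 months. That form suits a response event; it does not express how long SD must last.

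A reader might infer two further things that the documents do not support.

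- That responders always count under both definitions. This holds only if the 6-month condition in 10.2 attaches to SD alone, and the sentence can be read either way.
- That the 10.3.2 time frame must become 18 months. The window "between 8 weeks after starting therapy (C3D1) through 18 months after starting therapy" belongs to item 2 of 10.2, objective response. Item 4 does not repeat it. If the 6-month condition governs response too, an 18-month frame would be wrong.

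**Conclusion.** The inconsistency is real. A subject with SD at week 8 who progresses before 6 months without responding counts under 10.3.2 and not under 10.2, on either reading of 10.2. With complete scans, 10.3.2 can only match or exceed 10.2. This rests on the text and needs no assumption about rates.

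The size is illustrative: 19 to 32 percentage points, or at most about 2.2 to 3.9 of 12 subjects. It assumes exponential progression-free survival with medians borrowed from another drug pair, and treats all subjects as assessable by RECIST, although bone-only disease is eligible and 10.2.1 does not use RECIST for response there. It should not be read as a prediction that the reported count will be too high by that much.

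The consequence is limited to one descriptive secondary count in 3 to 12 evaluable subjects, reported by final dose level. The dose decision in 12.4 rests on dose-limiting toxicities and is untouched.

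**What to change.** - Replace the 10.3.2 wording with the 10.2 definition, so that SD counts only if maintained without progression to the 6-month assessment.
- In both sections, state whether the 6-month condition also applies to objective response. The sponsor has to choose. Whether a week-8 responder who progresses at week 16 should count as a durable benefit is the case to decide on.
- Set the 10.3.2 time frame to match that choice.
- Name the scheduled scan that serves as the 6-month assessment, for example week 24 (± 7 days), since none falls exactly at 6 months. In the illustration, taking week 24 or exactly 6 months moves the progression-free share by 2 to 3 points (0.704 − 0.683 and 0.499 − 0.470).

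How SD and progression are judged in bone-only disease is a separate question and should be raised on its own.

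The cost is a wording amendment to 10.2 and 10.3.2, submitted to the IRB as a modification under 11.1. No scans or data are added. The reported count may be lower.
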